6.4 Survey

Through the baseline, 6-month (-2 weeks/+4 weeks) and 12-month (-2 weeks/+4 weeks) surveys, we will ascertain key demographic data, health insurance coverage, income, other household information, self-report of unmet basic needs, and resources for addressing financial burdens currently being utilized. Via self-report measures, we will also assess communication with health care professionals, navigation and uptake of resources, and financial management behaviors.^{5,39} We will also obtain self-report information about participants' clinical history, including polypharmacy. We will also include validated survey measures to assess depressive

symptoms and diabetes-related distress (DDS⁵⁴), and health literacy. All other measures are identified throughout the surveys. Primary and secondary outcomes are shown below in Table 2.

Research staff will collect survey data via a computer-assisted interview. In-person interviews will take place in a private room located at Domino's Farms or other University of Michigan location. Patients will be provided with detailed directions to the space. Interviews conducted as a virtual appointment will take place via phone. All research staff will complete PEERRS and Good Clinical Practice training as well as training on best practices in data collection from the study Project Manager and Recruitment Coordinator. Through the use of trained research staff to administer the study, we anticipate being able to collect the most complete data possible. We do not anticipate any foreign language concerns in administering the survey. All efforts will be made to ensure that study materials including the survey are in plain language. Additionally, the survey will be administered by research staff, so no reading of the survey will be required by patients.

	Measures	Outcome
Primary Outcomes	HbA1c	
 Change in HbA1c will be measured at baseline, 6 months, and 12 months using HbA1c machine. HbA1c is a measure of the average level of glucose in blood over the past 3 months measured as a percentage.
Secondary Outcomes	Blood Pressure	
 Change in blood pressure will be measured at baseline, 6 months, and 12 months using an automated blood pressure machine. Blood pressure is measured as systolic blood pressure/diastolic blood pressure in millimeters of mercury (e.g., 120/80 mm Hg).
	Cost-related nonadherence behaviors with prescribed treatment regimens related to diabetes	
 Cost-Related Non-Adherence (CRN) Behaviors related to diabetes will be measured at baseline, 6 months, and 12 months by 4-items adapted from the Medicare Current Beneficiary Survey and 2 items adapted from the National Health Interview Survey that look at diabetes. The items are measured with a 4-point Likert scale. Participants answering "often" or "sometimes" to any of the items are indicated as exhibiting CRN.
	Cost-related nonadherence behaviors with prescribed treatment regimens related to other conditions being managed	
 Cost-Related Non-Adherence (CRN) Behaviors related to other conditions being managed will be measured at baseline, 6 months, and 12 months by 4-items adapted from the Medicare Current Beneficiary Survey and 2 items adapted from the National Health Interview Survey that look at other health conditions being managed. The items are measured with a 4-point Likert scale. Participants answering "often" or "sometimes" to any of the items are indicated as exhibiting CRN.
	Perceived financial burden	
 Perceived Financial Burden will be measured at baseline, 6 months, and 12 months by the 12-item measure Comprehensive Score for Financial Toxicity (COST) – Functional Assessment of Chronic Illness Therapy (FACIT). The items are measured with a 5-point Likert scale. The higher the score the better the Financial well-being.
	Unmet Social Risk Factors	
 Change in Unmet Social Risk Factors will be measured at baseline, 6 months, and 12 months by 20 items adapted from the Accountable Health Communities Health-Related Social Needs Screening Tool, the Health Leads Social Needs Screening Toolkit, and the Kaiser Permanente Your Current Life Situation Questionnaire. The item values are binary (yes/no). Number of "yes" responses indicates number of unmet social risk factors.
	Unmet Social Risk Factors	
 Change in Unmet Social Risk Factors will be measured at baseline, 6 months, and 12 months by 3 items from the Accountable Health Communities Health-Related Social Needs Screening Tool and 1 item adapted from the National Health Interview Survey. The items each have three response options, in which a positive response indicates an unmet social risk factors.

7 DATA COLLECTION AND MANAGEMENT PROCEDURES

7.1 Data collection

Participants will complete 3 data collection appointments. Each appointment will last approximately 90 minutes and will consist of a survey assessment, an HbA1C test, and two blood pressure readings. Participants enrolled prior to AME00101220 were enrolled in-person and completed surveys and assessments in-person; following AME00101220 all surveys and assessments for all participants are conducted virtually via phone. The baseline survey will be

given to participants prior to randomization. At the baseline appointment participants randomized to the intervention group will be asked to engage with the CareAvenue website on a tablet provided for use on-site or on own personal devices for virtual appointments. They will be asked to complete the website, which will take up to 20 minutes, and will also be provided a unique username and ID to login to the website on their own time.

Trained research staff will collect survey data via a computer-assisted interview through the use of Qualtrics software. We will assess HbA1c with an HbA1c machine. For in-person appointments research staff will be trained in best practices for HbA1c assessment by staff of the University of Michigan Department of Pathology. Once trained, research staff can train additional staff on use of the HbA1c machine. The HbA1C reading will be entered into Qualtrics. We will take the participant's blood pressure readings using an automatic blood pressure monitor. The blood pressure readings will also be entered into Qualtrics. Participants completing virtual appointments will obtain these measurements using at-home testing supplies provided by the study team.

All data will be downloaded from Qualtrics into a CSV file. This file will then be uploaded into SAS to create the study database.

7.2 Process evaluation

On a regular basis once the intervention is deployed, a research staff member will monitor resources being promoted. We will measure program engagement by completed IVR calls and web analytics data (e.g. unique log-ins, time on page, click throughs, etc).

We will also assess experience with the program with a purposive sample of intervention participants selected based on differing levels of engagement with the intervention.

7.3 Data Safety

The Data Manager will audit data collection processes on a weekly basis in order to ensure study procedures related to data safety are being followed. Any issues will be reported to the Project Manager and PI within 24 hours of identifying the problem. Weekly meetings will be held between the Project Manager and research staff and data collectors to provide an opportunity for discussing general interviewing issues and issues of confidentiality. The Project Manager will report directly to the PI on a weekly basis or per the adverse event timeline available in the DSMP in Appendix 5.

Only the Project Manager, Data Manager, and Recruitment Coordinator will have access to data and participant identifiers. All other research staff, including the data collection staff, and the investigators will only have access to specific and select information on an 'as needed' basis in order to conduct recruitment, data collection, or the intervention.

All data collected will be coded so that no direct participant identifiers are linked with the data. Access to the code that links data with participant identifiers will be held only by the Data Manager and Project Manager. All electronic files will be stored on the U:\ drive, the HIPAA-compliant MiStorage service with the Common Internet File System (CIFS) protocol on storage appliances from NetApp and EMC, maintained by the University of Michigan Information and Technology Services at the University of Michigan in the Michigan Academic Computing Center (MACC). The MACC is a highly secure data center with advanced facility security systems including card scanning systems, cameras, closed circuit television, and monitoring to restrict access to appropriate Data Center Operations personnel and approved faculty and staff. Physical access to the server is limited to trained and authorized system administrator employed by ITS.

Participant data for IVR calls will be maintained by a HIPAA-compliant platform within the University of Michigan Health System. All participant data collected and transmitted through the intervention website will be sent encrypted via TLS/SSL secure transfer.

SMS participant data will be stored on HIPAA-compliant University of Michigan servers. In order to send and receive SMS messages, the SMS platform will transmit and receive messages through Twilio. Messages will be automatically redacted on Twilio's servers, to ensure that participants' messages and identifiable data such as phone numbers are not stored in Twilio's logs. The CareAvenue website will not have access to any participant identifiers. The website will only collect responses to content questions and progress of website completion. Progress of website completion will be securely transmitted through an application programming interface hosted on a HIPAA-compliant server within University of Michigan Health System and will be encrypted using TSL or SSL encryption.

Some virtual appointments may be conducted with a HIPAA-compliant tele-meeting program used at the University of Michigan. The virtual study appointments will be audio only; no audio content of the call will be saved.

When data must be shared for study purposes (e.g. potential Diabetes Registry patient lists, reports to the DSMB), it will be shared through the University of Michigan School of Public Health secure, HIPAA-compliant fax line or stored virtually via a secure, HIPAA-compliant web application hosted by the University of Michigan, DropBox at U-M, or through MiShare, a secure virtual file transfer system hosted by Michigan Medicine Health Information Technology & Services (HITS).

To the extent that logbooks or paper records for individual participants need to be maintained for purposes of data collection or conducting the intervention, they will be kept locked in file cabinets in a locked room accessible to research staff only. All consent forms will be stored in the same manner. All participant identifiers will be destroyed as soon as it is no longer needed for completion of study related activities.

8 DATA ANALYSIS

All primary analyses will be intention-to-treat. From our prior work, we expect low rates of missing data. We will use multiple imputation on any variables with >5% missingness in linear mixed-effects models. We will apply the inverse probability weighting method to GEE models to handle dropout cases to perform complete case analysis. We will conduct sensitivity analyses to assess any impact of missing data.

8.1 Preliminary analyses

We will examine baseline clinical differences between study arms and use them as model covariates as appropriate to address potential uncontrolled confounding. We will use t-tests and analysis of variance (ANOVA) to assess effects of covariates (e.g., gender, age, education, health insurance type) on continuous outcomes (e.g., HbA1c). For categorical variables, we will calculate two-way contingency tables (e.g. % improved by arm), and use odds ratios and chi-square tests to evaluate differences in proportions by study arm. These results will be used to guide multivariate regression analyses.

8.2 Regression models

For the primary outcome (HbA1c), we will fit a longitudinal mixed-effects model to all repeated measurements during the pre-randomization baseline period and the one-year intervention period. The model will have the intervention (yes/no) as the main independent

variable and HbA1c accounted for as a repeated measure within patients. Thus, we will model HbA1c as a function of fixed effects for the treatment arm (the intervention group vs. the control group), the observation period (baseline vs. one-year intervention period), and a treatment-by-time period interaction term, with adjustment for confounding covariates (age, gender, race, income, health insurance type, comorbidities, health literacy). For this model, the coefficient of the treatment-by-time period interaction effect estimates the key parameter of interest: changes in HbA1c levels. Random effects are included in the model to adjust for HbA1c variation over time within patients. We will take a similar modeling approach to secondary outcome measures (CRN behaviors, perceived financial burdens, perceived stress of unmet SDHs). We will also dichotomize outcomes based on standard thresholds (eg., baseline HbA1c 8-9% vs > 9%) and use similar mixed-effects logistic regression models to test differences in HbA1c, CRN behaviors, perceived financial burdens, and perceived stress of unmet SDHs across treatment arms.

Among those randomized to CareAvenue in Aim 1, we will assess the change in magnitude of the outcome coefficient's association with the intervention before and after the adjustment of mediators of interest (see Figure 1, conceptual model). We will examine the Lagrange Multiplier and Wald Tests to consider the deletion or inclusion of paths based on our hypotheses.⁵⁶ Once the model is identified, we will test for group differences (i.e. intervention vs. control) in latent constructs and in the paths between these constructs. This method will allow us to estimate the intervention effects on the constructs directly as well as their relationships to one another.⁵⁶ We will follow guidelines for adequate reporting of SEM using three goodness-of-fit indices: Bentler-Bonnet's Normed Fit Index (NFI), Bentler-Bonnet's Non-Normed Fit Index (NNFI), and the Comparative Fit Index (CFI). We will also verify the root mean-square error of approximation (RMSEA) as an index of misfit. Well-fitting models will have fit indices of .90 or higher and <.06 for RMSEA.

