2 OBJECTIVES

The overall objective is to determine the extent to which activating patients to address health-related financial burdens that impact treatment adherence and unmet SDHs improves disease control, and the mechanisms through which primary and secondary outcomes are achieved. The specific aims of the study are listed below.

Aim 1: Determine the effectiveness of CareAvenue relative to usual care in improving glycemic control and patient-centered outcomes such as CRN behaviors and perceived financial burdens. We hypothesize that participants randomized to CareAvenue will have a change in HbA1c (**primary outcome**) compared to usual care. We will measure the change in HbA1c at baseline, 6 months (-2 weeks/+4 weeks), and 12 months (-2 weeks/+4 weeks) using an HbA1c machine. Additionally, we hypothesize that other patient-centered outcomes (**secondary outcomes**) will change compared to usual care. Secondary outcomes will be measured at baseline, 6 months (-2 weeks/+4 weeks), and 12 months (-2 weeks/+4 weeks). They include blood pressure (measured with an automated blood pressure cuff), Cost-related non-adherence behaviors with prescribed treatment regimens related to diabetes, Cost-related non-adherence behaviors with prescribed treatment regimens related to other conditions being managed, Perceived financial burden, and unmet social risk factors.

Aim 2: Examine mediators and moderators of the effectiveness of CareAvenue on primary and secondary outcomes. We hypothesize that the intervention will significantly improve skills and self-efficacy in uptake and use of resources leading to decreased financial burdens, perceived stress of unmet SDHs, and improved adherence to treatment regimens, with these changes being the primary mechanism through which improvements in glycemic control are achieved. We also hypothesize that CareAvenue will be most effective among patients with high need for resources and low self-efficacy in navigating resources at baseline.

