4.1 Inclusion and Exclusion Criteria

Study participants will meet the following criteria:

- 18-75 years of age
- Have access to a telephone that can receive and send text messages
- diagnosis of diabetes with prescribed anti-hyperglycemic medication
- most recent (within the past 6 months) recorded hemoglobin A1c (HbA1c) level of $\geq 7.5\%$ for individuals ≤ 70 years and $>8.0\%$ for individuals between 70-75 years in age
- positive report of financial burden or CRN using screening questions developed and validated from prior work³³⁻³⁷

Exclusion criteria include significant cognitive impairment precluding individuals from completing the study as evidenced by ability to complete study intake procedures and current participation in another diabetes study.

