10 STATISTICAL CONSIDERATIONS

The calculations used to determine study sample size for detecting differences between study arms at follow-up in our primary outcome of HbA1c are based on early data collected in the study. The hypothesis to be tested is that the intervention will lead to uptake of low-cost resources for health and unmet basic needs and reductions in CRN, thus leading to medication/regimen adherence and intensification. We expect the beneficial impacts from improved access to treatment recommendations and unmet basic needs can lead to improved HbA1c management and control. A 0.5 or greater reduction in HbA1c, after adjusting for

confounding covariates, is considered a clinically meaningful change in stabilizing or improving HbA1c control.⁵⁴ We designed the study to have 80% power at an alpha level of 0.05 to detect a change difference of 0.53 unit change in hemoglobin HbA1c between study arms, and a standard deviation of 1.46. This is based on early data collected in the study.⁵⁵ We will need a total of 510 participants (255 per arm) with outcome data to show a 0.53 unit difference in HbA1c. With this sample size, we will also have sufficient power to detect differences in our other self-reported secondary outcomes.

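### The primary HbA1c model merges the 6- and 12-month visits, so it gives no effect at either one, and it does not use the arms' common pre-randomization mean.

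*Combined protocol and SAP*

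**What the plan says.** - Section 2, Aim 1: "We will measure the change in HbA1c at baseline, 6 months (-2 weeks/+4 weeks), and 12 months (-2 weeks/+4 weeks) using an HbA1c machine".
- Section 8.2 fits a mixed model to "all repeated measurements during the pre-randomization baseline period and the one-year intervention period". Baseline HbA1c is therefore one of the responses. The fixed effects are treatment arm, "the observation period (baseline vs. one-year intervention period), and a treatment-by-time period interaction term".
- The estimand in Section 8.2 is a single number: "the coefficient of the treatment-by-time period interaction effect estimates the key parameter of interest: changes in HbA1c levels".
- The covariates in Section 8.2 enter "with adjustment for confounding covariates (age, gender, race, income, health insurance type, comorbidities, health literacy"). Baseline HbA1c is not among them.
- Section 8: "We will use multiple imputation on any variables with >5% missingness in linear mixed-effects models".
- Section 10 bases the sample size on "detecting differences between study arms at follow-up in our primary outcome of HbA1c" and names no month.

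No section gives a three-level visit term, a 6- or 12-month contrast, a primary time point or a shared baseline mean. Section 8.1 adds baseline differences as covariates only where judged appropriate after they have been inspected.

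**The concern.** There are two separate points.

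**Merged visits.** With a two-level time factor, one coefficient covers both follow-up visits. Text messages run for 52 weeks, while the website is first used at the baseline appointment, so whether any benefit lasts to 12 months is a real question. The primary model cannot answer it. Visit-specific effects added after the data are seen would be post hoc.

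**Unused baseline information.** Baseline is measured before randomization, so the arms have the same expected baseline mean. An arm main effect leaves those means free, and the interaction becomes a plain difference in change. It is unbiased but usually less precise than an estimate that uses the common mean or adjusts for baseline. This point, not the merging of visits, costs precision. At stake are the width of the confidence interval and the ability to detect effects smaller than the design difference.

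**Working it through.** **Inputs.** Section 10 gives a difference of 0.53, SD 1.46, 255 per arm with outcome data, 600 recruited (300 per arm), and expected response of 94% at follow-up 1 and 80% at follow-up 2. The within-patient correlation ρ is not given, so 0.3 to 0.7 is assumed. The SD is read as the per-visit SD, and alpha as two-sided.

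**The plan's own figure.** n per arm = 2(1.960 + 0.842)² × 1.46² / 0.53² = 119.1, so 120 per arm, not 255. The stated size is approached if 1.46² = 2.13 is entered as the SD (253.9, so 254 per arm). The documents do not show whether that was done. It is a separate matter. The variance factors below do not depend on the SD, but the absolute SEs and powers do.

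**What the merged coefficient reports.** Complete data give weights of 0.50/0.50. Independent 94%/80% attendance at ρ = 0.5 gives about 0.55/0.45. The true effects below are illustrative.

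| Effect at 6, 12 months | Equal weights | 94%/80% attendance |
|---|---|---|
| 0.25, 0.53 | 0.390 | 0.376 |
| 0.10, 0.53 | 0.315 | 0.293 |
| 0.53, 0.10 | 0.315 | 0.337 |

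A building effect and a fading effect are identical under equal weights. Attendance moves the coefficient by only 0.014 to 0.022, and the imputation in Section 8 would bring the weights back to about equal.

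**Precision of the year-average, complete data, equal variances, exchangeable correlation.**
- Free baseline means: Var = (2σ²/n)[(1+ρ)/2 + 1 − 2ρ] = 3(1−ρ)σ²/n.
- Common baseline mean: Var = (2σ²/n)[(1+ρ)/2 − ρ²] = (1−ρ)(1+2ρ)σ²/n.
- Ratio: (1+2ρ)/3.

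At ρ = 0.5 and n = 255, the free-baseline SE is √(3 × 0.5 × 2.1316/255) = 0.112. The common-baseline SE is √(0.5 × 2 × 2.1316/255) = 0.091. The 95% half-widths are 0.22 and 0.18.

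| ρ | 255/arm complete: free, common SE (factor) | 300/arm, 94%/80%: plan, proposed SE (factor) |
|---|---|---|
| 0.3 | 0.1325, 0.0968 (0.53) | 0.1258, 0.0945 (0.56) |
| 0.5 | 0.1120, 0.0914 (0.67) | 0.1066, 0.0887 (0.69) |
| 0.7 | 0.0867, 0.0776 (0.80) | 0.0828, 0.0748 (0.82) |

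The last column uses generalized least squares with independent attendance. It compares the plan's coefficient with the equal-weight contrast under a common baseline.

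**Narrower baseline spread.** Section 4.1 requires a minimum on the "most recent (within the past 6 months) recorded hemoglobin A1c (HbA1c) level", which may reduce the baseline SD to a fraction r of the follow-up SD. The free-baseline bracket becomes (1+ρ)/2 + r² − 2ρr and the common-baseline bracket is unchanged. The two differ by (r − ρ)², so the gain vanishes when r = ρ. For example, r = 0.7 and ρ = 0.5 give 0.50/0.54 = 0.93.

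| r | ρ = 0.3 | ρ = 0.5 | ρ = 0.7 |
|---|---|---|---|
| 0.9 | 0.61 | 0.76 | 0.90 |
| 0.8 | 0.69 | 0.85 | 0.97 |
| 0.7 | 0.78 | 0.93 | 1.00 |

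**Power, ρ = 0.5, 255 per arm, SD 1.46.** At a year-average of 0.53, both models exceed 99%. At an assumed 0.30, power is 76% with free baselines and 91% with a common one.

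**The case against.** The strongest reply is that nothing here is an error. The merged coefficient is unbiased, Aim 1 and the power text both speak of change, and a longitudinal model with free baseline means is standard. The plan does not forbid visit-specific estimates, and it states no hypothesis about timing. All of that stands. This is a gap in what is prespecified plus an avoidable loss of precision, and type I error is unaffected.

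The size of the precision gain is also uncertain, because neither ρ nor the baseline SD ratio is in the documents. That stands too: the gain runs from large to none. Combining r = 0.7, ρ = 0.7 and 94%/80% attendance, the proposed SE is marginally larger (0.0748 against 0.0746, factor 1.005), because equal weights replace attendance-driven ones.

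Three inputs are soft:
- The 94%/80% figures are survey response rates, listed beside a 12% loss allowance, and not stated HbA1c attendance.
- The 0.30 effect is an assumption below the 0.5 that Section 10 calls clinically meaningful.
- The SD of 1.46 may belong to the change score. In that case 2(1−ρ)σ² = 1.46², and the free-baseline SE at 255 per arm is √(1.5 × 2.1316/255) = 0.112 at every ρ, with the same variance factors. If the SD were the 2.13 that nearly reproduces 510, power at 0.53 and ρ = 0.5 would be 90% with free baselines against 98% with a common one.

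None of this supplies the missing 6- and 12-month effects or a reason to ignore the common baseline. Section 8.1 is not a remedy, since it makes adjustment depend on observed imbalance and does not name baseline HbA1c.

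**Conclusion.** The concern holds, as something that should be changed rather than a fault that invalidates the trial. The reading of Section 8.2 is firm: there are two time levels, one coefficient, a free arm effect at baseline, and no baseline HbA1c covariate. The primary result cannot distinguish a building effect from a fading one.

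The precision loss is conditional. Under equal variances and ρ of 0.3 to 0.7, a common baseline cuts the variance of the year-average by 20% to 47%. If the baseline SD is 0.7 to 0.8 of the follow-up SD, the cut is 22% to 31% at ρ = 0.3, 7% to 15% at ρ = 0.5, and 0% to 3% at ρ = 0.7. With SD 1.46, power for 0.53 is already high, so the benefit lies in narrower intervals and smaller detectable effects.

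**What to change.** In Section 8.2:

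1. Code time as baseline, 6 and 12 months, with an unstructured within-patient covariance.
2. Include arm-by-6-month and arm-by-12-month terms and drop the arm main effect, so that both arms share one baseline mean. Alternatively, take baseline out of the response and adjust the follow-up values for baseline HbA1c.
3. Keep the year-average as primary, defined as the fixed equal-weight contrast of the two arm-by-visit terms.
4. Report the 6- and 12-month effects with confidence intervals from the same fit.
5. Name in Section 10 the contrast to which the sample size refers.
6. Apply the same coding to the secondary outcomes, because Section 8.2 extends its approach to them.

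The cost is SAP wording and one model statement. No new data or participants are needed. With the year-average kept as primary, the SE was smaller or equal in every case computed except the trivial one noted above.

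The sponsor may prefer 12 months as primary. That is a choice of estimand and brings no precision gain. At 300 per arm with 94%/80% attendance and equal variances, the 12-month SE with a common baseline would be 0.127, 0.114 and 0.094 (ρ = 0.3, 0.5, 0.7), against 0.126, 0.107 and 0.083 for the current coefficient.

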Intervention participants will be asked to give their provider their CareAvenue-generated action-plan to alert them of their needs and possibly receive additional support in accessing services. Although the intervention is targeted at the individual, physicians may change their behavior based on their interaction with treatment group patients and begin to better address unmet needs with control patients, thus raising the issue of contamination. That is, due to interactions with intervention patients, providers may alter “usual care.” This could diminish the effect size between intervention and control patients. One solution to this problem would be to conduct a cluster-randomized trial, which would obviate such contamination. We concluded, however, that because of the large number of unique providers seeing patients in the Diabetes Registry, the likelihood that a doctor will have patients in each arm is low. Further, some cross-over is inevitable because many patients in the Diabetes Registry see both a specialist and primary care provider, who may be randomized to different arms. Finally, a cluster randomized design would have required a large increase in sample size and cost. Although potential contamination lowers the treatment effect, we consider our design a strength of the study compared to a cluster randomized trial because baseline and follow-up assessments will allow us to quantify how much the control group also benefited from increased communication about low-cost treatment options with providers in the absence of the e-Health tool (comparing pre- and post- data among control patients within providers). This will demonstrate a generalized effect for the whole practice. We have increased the sample size by 3% to account for the potential that physicians’ behavior will spill over onto control patients. To account for a potential 12% loss to follow-up, we will recruit 600 participants. Based on our preliminary data from the pilot study and co-investigators’ prior studies with this population, we expect the following survey response rates: recruitment (72%), baseline (87%), follow-up 1 (94%), and follow-up 2 (80%).

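### On the natural reading of Section 8.2, the seven covariates adjust HbA1c level and not HbA1c change, so the primary result labelled adjusted is essentially unadjusted

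*Combined protocol and SAP*

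**What the plan says.** Section 8.2 fits one mixed model to all HbA1c measurements, so baseline HbA1c is an outcome row and not a covariate. The fixed effects are arm, period (baseline against the intervention year) and "a treatment-by-time period interaction term, with adjustment for confounding covariates (age, gender, race, income, health insurance type, comorbidities, health literacy". The section then states that "the coefficient of the treatment-by-time period interaction effect estimates the key parameter of interest: changes in HbA1c levels". No other interaction is named, and the structure of the random effects is not given. Secondary outcomes are to be modelled in much the same way.

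Other sections bear on this:

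- Section 8.1 would examine baseline differences between arms and "use them as model covariates as appropriate to address potential uncontrolled confounding".
- Section 10 introduces its clinically meaningful change with "A 0.5 or greater reduction in HbA1c, after adjusting for" confounders.
- Section 6.4 collects income and health insurance at baseline, 6 and 12 months. Section 8.2 does not say which values enter the model.
- Section 8 prescribes multiple imputation for variables with more than 5% missing. Section 10 expects 94% and 80% response at the two follow-ups.

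**The concern.** The primary parameter is a difference between arms in change from baseline. A main effect of a covariate that is fixed per patient adds the same amount to that patient's baseline and follow-up values, so it cancels from the change. The adjustment that Sections 8.1, 8.2 and 10 all refer to would then not act on the parameter being reported.

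Two things are at stake. The trial would report an effect as adjusted for age, income, insurance and the rest when it is in substance the raw difference in change. A chance imbalance in something that predicts HbA1c change would also stay in the estimate, and any precision those covariates could give would go unused. The same holds for continuous secondary outcomes and for any covariate added in this form under Section 8.1.

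**Working it through.** **1. Algebra.** Write the model for patient i at visit t as

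Y = a + b·Arm + c·Period + d·Arm·Period + X'θ + error,

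with X fixed per patient. Subtracting baseline from follow-up gives an expected change of c + d·Arm, in which X'θ is absent. With every visit observed and one covariance for all patients, the model splits into a level part (regressors 1, Arm, X) and a change part (regressors 1, Arm). The regressors of the change part are a subset of those of the level part, so joint generalised least squares for d reduces to the difference between arms in mean change, whatever X is.

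**2. Complete data.** Simulated, three visits, seven covariates that predict both level and change:

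| Check | d, no covariates (SE) | d, seven main effects (SE) |
|---|---|---|
| 510 patients, compound symmetry | -0.348915 (0.076696) | -0.348915 (0.076696) |
| 510 patients, unstructured covariance | -0.346811 (0.077865) | -0.346811 (0.077865) |
| Deliberate 0.3 SD arm imbalance in one covariate | -0.26896 (0.08944) | -0.26896 (0.08944) |

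In the last row, covariate-by-period terms moved the estimate to -0.28662. In fitted mixed models with 600 patients, the estimates with and without main effects differed by less than 1e-12.

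**3. Missing data.** Response of 94% and 80% means 6% and 20% missing. If HbA1c is missing at those rates, both follow-ups exceed the 5% threshold for imputation. Each completed dataset is balanced, so step 2 applies within it, and covariates can act only through the imputation model. For data analysed as observed, with 600 simulated patients:

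| Dropout | Shift in d from adding main effects | SE ratio |
|---|---|---|
| 6% and 20% missing (25 trials per setting) | max 0.007 | 1.000 to 1.001 |
| 12% random loss (40 trials) | mean 0.006, max 0.017 | 0.997 |
| Loss dependent on a covariate, more strongly in one arm (40 trials) | mean 0.014, max 0.036 | 0.998 |

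In the last, deliberately adverse scenario the simulated truth was -0.30. The average estimate was -0.353 without covariates, -0.339 with main effects and -0.296 with covariate-by-period terms, whose SE was about 5% smaller than without covariates.

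**4. Time-varying values.** If a covariate is re-measured and is itself affected by arm, the invariance fails. In one simulated dataset d moved from -0.429 to -0.354. That would be adjustment for a post-randomisation variable.

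**5. Possible precision gain.** With covariate-by-period terms the SE scales by about √(1 - R²), where R² is the share of the variance of change explained. The documents give no R², so the range below is an assumption.

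The starting power also needs care. Section 10 says "We designed the study to have 80% power at an alpha level of 0.05 to detect a change difference of 0.53 unit change" "and a standard deviation of 1.46", and "We will need a total of 510 participants (255 per arm) with outcome data to show a 0.53 unit difference in HbA1c". Assuming a two-sided test and that 1.46 is the SD of change, n per arm = 2 × (1.960 + 0.842)² × 1.46² / 0.53² = 119.1, that is 120 and not 255. At 255 per arm, power = Φ((0.53/1.46) × √(255/2) - 1.960) = Φ(2.139) = 98.4%. With an SD of √2 × 1.46 it is 82.6%. The table therefore gives two starting points, the stated 80% (power = Φ(2.802/√(1 - R²) - 1.960)) and 98.4%.

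| Assumed R² | SE factor | Power from 80% | Power from 98.4% |
|---|---|---|---|
| 5% | 0.975 | 82% | 98.8% |
| 10% | 0.949 | 84% | 99.1% |
| 20% | 0.894 | 88% | 99.6% |

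**The case against.** The strongest reply is that Section 8.2 speaks only of adjustment and does not fix the functional form. It never says main effects only, and it never says that income and insurance are held at baseline. This stands: both premises are inferred. But no covariate-by-period term is written, so an analyst following the text would fit main effects. The alternative of entering re-measured values would bring in post-randomisation adjustment, which is a further reason to specify.

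It is also fair to say that the invariance is exact only for complete or completed data. Under dropout analysed as observed the coefficient does move, by up to about 0.04 HbA1c points in the adverse scenario, and there it moved towards the truth. That is still small beside the design difference of 0.53.

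A reader might infer that the primary estimate is biased. The documents do not support that. Arms are randomised, the unadjusted difference in change is free of confounding, and its standard error already allows for chance imbalance. Section 10's mention of adjustment describes a clinically meaningful change and is not a model specification that Section 8.2 breaks.

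A reader might also infer a material loss of power. The documents contain no correlation between the covariates and HbA1c change. If 1.46 is the SD of change, the gain is about one point at most over the range shown.

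**Conclusion.** The point holds as one of labelling and efficiency. As Section 8.2 is naturally read, its covariate adjustment does not reach the treatment-by-period coefficient: exactly so with complete or imputed data, and nearly so with the expected dropout. The result would be reported as covariate-adjusted while being essentially unadjusted.

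This rests on covariates that are fixed per patient and entered as main effects, and on a covariance structure common to all patients. The size of the forgone precision is unknown. For R² of 5% to 20% it would be 2 to 8 points of power starting from 80%, and 0.4 to 1.2 points starting from 98.4%. That main effects do not adjust the change needs no assumption about R².

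**What to change.** In Section 8.2:

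- State that the seven prespecified covariates enter at their baseline values, including income and insurance, which are measured again at follow-up.
- Add a baseline-covariate-by-period term for each, with continuous covariates centred and categorical ones sum-coded, to the primary HbA1c model and the models for continuous secondary outcomes. A model of follow-up HbA1c on baseline HbA1c and the same covariates would serve equally well.
- Keep the covariate list fixed in advance.
- If neither change is made, describe the primary estimate as unadjusted.

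No new data are needed. The cost is a sentence or two and some extra parameters, more than seven once race, income and insurance type are coded. If the covariates do not predict change, the standard error widens by the order of 0.5% to 1%. The simulations with uninformative covariates gave 0.5%. In the fixed-covariance check, where the variance is not re-estimated, it was 0.077438 / 0.076696, or 1.0%.
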